- Upon a subject's completion of the study (visit 8), in order to facilitate continuation of care by a non-study clinician

Monitoring of Study/Oversight:

Study staff will monitor source data and case report forms by regular internal monitoring. .

IRB Review/Ethical Conduct of Study:

IRB Review: Prior to enrolling any subjects, documentation will be obtained that the study protocol and informed consent form have been approved by the Rush University Medical Center Institutional Review Board. Any change in the protocol or informed consent form will require prior written approval except to prevent injury or risk to a subject.

Regulatory Considerations: This study will be conducted in accordance with the ethical principles stated in the most recent version of the Declaration of Helsinki or the applicable guidelines on good clinical practice, whichever represents the greater protection of the individual.

Informed Consent: The informed consent document, in conjunction with verbal discussion of the protocol, will be used to explain the study, including the risks and benefits, to the subject in simple terms before the subject is entered into the study. The investigator is responsible to see that informed consent is obtained from each subject and to obtain the appropriate signatures and dates on the informed consent document prior to the performance of any protocol procedures and prior to any changes made to a subject's medical treatment plan for the purpose of study participation. The original signed consent form will be retained by the investigator.

Confidentiality:

All information collected about subjects for the purposes of this study will be treated as confidential to the extent allowed by law. The information obtained while subjects are enrolled in this study, including all study-related hospital and office records, will be made available to the study doctor, Bristol-Myers Squibb, the Institutional Review Board and other regulatory agencies, including the United States Food and Drug Administration (U.S. FDA).

Intended Use of Data:

The results of this research project may be presented at meetings or in publications, but the identity of subjects will not be disclosed in such presentations.

Statistical Analysis:

Study Assessments and Primary Endpoints: The difference in absolute change in score from baseline to endpoint in the MGH-CPFQ between the MSA and the PBO groups is the primary endpoint. Key secondary endpoints will be difference in absolute change from baseline in MADRS score between MSA and PBO, difference in remission rates (MADRS < 11) between MSA and PBO, the change from baseline in total score at endpoint of MGH-CPFQ item analysis, difference in change scores on the CGI-S, CGI-I and QIDS. Safety outcome measures: adverse events, physical examinations, vital signs; blood pressure, orthostatic; EKG; Rush Sexual Inventory (RSI).

Statistical Methods: The randomized sample includes all patients who are randomized. The Safety sample will include those randomized patients who received at least one dose of doubleblind study medication as indicated on the dosing record. The efficacy sample will include those patients in the safety sample who have at least one efficacy evaluation post-randomization. The last observation carried forward (LOCF) data set includes data recorded at a given visit after randomization, or, if no observation is recorded at that visit, data carried forward from the previous postrandomization visit. The LOCF data set is primary, and analysis of the observed case data set also will be conducted.

The primary analysis will compare pooled MGH-CPFQ response rates between PBO and MSA and PBO non-responders. Differences in response rates will be compared using the CMH General Association Test. Descriptive statistics on non-primary groups will be conducted.

This study seeks to estimate the strength of any statistically significant relationship, or effect size, in addition to statistical significance of found treatment effects.

Secondary Endpoints Analysis: Differences in remission (defined as an endpoint MADRS score <11) rates will be compared using the CMH General Association Test. Logistic regression analysis will be performed to explore the relationship between response and patients' demographics and prognostic variables including baseline QIDS score, gender, site, and age, etc. Similar analyses will be performed for remission.

Fig. 3	: Stud	y Proce	dures	Table
--------	--------	---------	-------	-------

			Treatment period 1			Treatment period 2			
Study Visit	V1 Screen	V2 Baseline	V3	V4	V5	V6	V7	V8	V9 F/UP
End of Week	-1	0	1	2	3	4	5	6	8
Day	-7	0	7	14	21	28	35	42	56
Informed consent	Х								
Demographic data	Х								
Medical and psychiatric history	Х	Х							
SCID	х								
Physical exam	Х								
Vital signs and weight	Х	Х	Х	Х	Х	Х	Х	Х	Х
EKG	Х								Х
Lab tests*, urine pregnancy test** and urine drug screen	х								х
MGH-ATRQ	Х								
Inclusion/exclusion criteria	Х	Х							
Randomization		Х							
Expectation ratings		Х							
Clinician-completed surveys:									
HDRS (17- and 28-item)	Х	Х						Х	
MADRS		Х	Х	Х	Х	Х	Х	Х	
CGI-S	х	Х							
CGI-I			Х	Х	Х	Х	Х	Х	
C-SSRS	х	Х	Х	Х	Х	х	Х	Х	х
Patient-completed surveys:									
MGH-CPFQ	Х	Х	Х	Х	Х	Х	Х	Х	
EWPS	х	Х	Х	Х	Х	х	Х	Х	
Fawcett EPI	Х	Х	Х	Х	Х	Х	Х	Х	
FASD	Х	Х	Х	Х	Х	Х	Х	Х	
HSQ 2.0	Х	Х	Х	Х	Х	Х	Х	Х	
PGI-S	х	Х							
PGI-I			Х	Х	Х	Х	Х	Х	
RSI	Х	Х	Х	Х	Х	Х	Х	Х	
QIDS-16	Х	Х	Х	Х	Х	Х	Х	Х	
SANS	Х	Х	Х	Х	Х	Х	Х	Х	
SDS	Х	Х	Х	Х	Х	Х	Х	Х	
SF-36	Х	Х	Х	Х	Х	Х	Х	Х	
Study drug dispensed		Х	Х	Х	Х	Х	Х	Х	
Study drug accountability			Х	Х	Х	Х	Х	Х	Х
Concomitant therapy	Х	Х	Х	Х	Х	Х	Х	Х	Х
Adverse events	Х	Х	Х	Х	Х	Х	Х	Х	Х

*Including CBC and CMP. If patient can produce lab results for CBC and CMP performed within the past 3 months, screening procedures may be waived. **For females of childbearing potential

- Angst J. (1992). How recurrent and predictable is depressive disorder? In: Montgomery S, Rouillon F, eds. *Long-term treatment of depression perspectives in psychiatry*. Chichester, UK: John Wiley & Sons Ltd., Vol. 3, p.13.
- Carvalho AF, Machado JR & Cavalcante JL (2008). Augmentation strategies for treatmentresistant depression. *Current Opinion in Psychiatry*, 22 : 7–12.
- Chiarello RJ & Cole JO (1987). The use of psychostimulants in general psychiatry. *Archives of General Psychiatry*, 44, 286-295.

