- 1. Primary outcome: The group treated with MSA adjunctive to ADT will show a greater mean change from baseline to endpoint in total score as compared to the group treated with placebo (PBO) adjunctive to ADT as measured by the
 - a. Massachusetts General Hospital Cognitive-Physical Function Questionnaire (MGH-CPFQ)
- 2. Secondary outcome:
 - a. MSA adjunctive to ADT will demonstrate clinically acceptable safety and tolerability, compared to placebo, based on
 - i. spontaneously reported adverse events and significant adverse events
 - ii. significant changes in blood pressure and pulse
 - iii. significant changes in weight
 - iv. significant changes in electrocardiogram
 - v. significant changes in the Rush Sexual Inventory
 - b. The group treated with MSA adjunctive to ADT will show a greater mean change from baseline to endpoint as compared to the group treated with PBO adjunctive to ADT as measured by the change on
 - i. MGH-CPFQ individual item analysis
 - ii. MADRS scores:
 - 1. Total score
 - 2. Subscales
 - 3. Individual item analysis
 - 4. Percent of "responders" (\geq 50% reduction in score baseline to endpoint)
 - 5. Percent reaching "remission" (score of ≤ 10 at endpoint)

- c. The group treated with MSA adjunctive to ADT will show statistically significant improvement in core residual symptoms of MDD extant on monotherapy ADT as measured by the
 - i. PGI (Patient Impression and Improvement) scales
 - ii. Quick Inventory of Depressive Symptomatology-16 (QIDS-16) total score (≤ 6) and subscale
 - iii. Clinical Global Impression-Severity (CGI-S); and, Clinical Global Impression-Improvement (CGI-I)
 - iv. QIDS total score and subscale
- d. The group treated with MSA adjunctive to ADT will show statistically significantly improvement in overall functioning (work, social and cognitive) when compared to the group treated with PBO and ADT as measured by the
 - i. Total and individual item scores from the HDRS-17 and -28
 - ii. Maier and other subscale scores from the HDRS-17 and -28
 - iii. Scale For Assessment Of Negative Symptoms (SANS)
 - iv. Health Status Questionnaire, 2nd ed. (HSQ 2.0)
 - v. SF-36 Health Survey (SF36)
 - vi. Fawcett Experienced Pleasure Index (EPI)
 - vii. Endicott Work Productivity Scale (EWPS)
 - viii. Sheehan Disability Scale (SDS)
 - ix. Fatigue Associated with Symptoms of Depression (FASD)

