- **Study Design:** A randomized, double-blind, placebo-controlled, parallel-group study of flexible dose mixed salts amphetamine (5-60 mg) adjunctive to antidepressant therapy among adult outpatients with major depressive disorder responding inadequately to current antidepressant therapy.

Fig. 1: Treatment Groups

Visit	Phase	Weeks	Group	Group	Procedures
		on med	1	2	
V1		Scr			Inclusion/Exclusion
V2		0			Baseline measurement + disp.
V3	Ι	1	MSA	PBO	Measure effect of 1 week on study med + disp.
V4	Ι	2	MSA	PBO	Measure effect of 2 weeks on study med + disp.
V5	Ι	3	MSA	PBO	Measure effect of 3 weeks on study med + disp.
V6	II	4	MSA	MSA	Measure effect of 3 weeks on study med + disp.
V7	II	5	MSA	MSA	Measure effect of 3 weeks on study med + disp.
V8	II	6	MSA	MSA	Measure effect of 3 weeks on study med
V9		(8)			Safety follow-up

Fig. 2: Study Design Overview

The treatment phase of the study consists of 2 phases (21 treatment days per phase). Study Phase 1 will consist of visits 2 (baseline) through 5. Study Phase 2 will consist of visits 6 through 8. There will be a follow-up visit 2 weeks following visit 8. There is a one-week interval between study visits, with a scheduling window of \pm 3 days allowed.

Mixed salts amphetamine is FDA-approved for Attention Deficit-Hyperactivity Disorder (ADHD) and superior in efficacy to placebo; therefore, comorbid ADHD will be statistically controlled as a continuously-variable covariate, but will not be considered an exclusionary condition.

The primary analysis will be a repeated measures analysis of variance using a mixed-effects model (PROC MIXED-MMRM). The primary outcome measure will be the MGH-CPFQ total score at baseline and the MGH-CPFQ total score at the end of the trial. The independent variables will be the study visit, the treatment in the previous phase, and treatment assignment. The variance covariance matrix for the repeated measures will be unspecified.

Enrollment Period: The enrollment period is estimated to be 6 months. The last patient is expected to complete the study by March 31, 2010.

Number of Subjects: 40 subjects will be randomized (20 to each treatment arm). Additional subjects may be consented to allow for screen failures. Subjects who terminate early post-randomization will be replaced only sufficiently to ensure a total number of 24 (12 to each treatment arm) evaluable subjects.

Duration of Subjects' Study Participation: There will be a total of 9 study visits over a period of 9 weeks.

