- 11) Pregnant or breastfeeding women.

Study Procedures: Figure 3 shows study procedures to be performed at each visit. No study procedures will be performed until a subject signs the informed consent document.

Screen visit (Visit 1): Medical and psychiatric history will be taken, a physical examination and vital signs will be performed and lab tests done. Lab tests include CBC, CMP, urine drug screen and urine pregnancy test for females of childbearing potential. If a subject has had the required lab tests performed within the past 3 months and can produce the results, lab procedures may be waived at the screening visit for that patient (except urine pregnancy test). The HDRS-17 score upon screening will be used to determine entry eligibility (see inclusion criteria). Beyond the patient's verbal report, we will attempt to obtain medical records (e.g., previous clinician or pharmacy records) to document adequate dose and duration of previous/current ADT.

Study Phase 1

Baseline visit (Visit 2): Screened and eligible subjects will return one week after the screening visit. At this visit (provided entry criteria continue to be met) subjects will be randomized in double-blind fashion to one of two treatment groups:

- Group 1: MSA during both phases; or
- Group 2: PBO during Phase 1 followed by MSA during phase 2

Study drug will be dispensed to the subject in sufficient quantity to last until the next study visit (7 days +/-3).

Study visits 3-5: Following the baseline visit, subjects will return at one-week intervals for study visits 3-5. Study procedures to be performed are reflected in Figure 3. Phase 2 study drug is dispensed at study visit 5.

Study visits 6-8: Subjects will return at one-week intervals for study visits 6-8. Study procedures to be performed are reflected in Figure 3. At visit 8, all subjects will receive instructions for tapering the dose of the MSA to avoid potential difficulties from abrupt discontinuation of the study drug.

Study visit 9: Subjects will return two weeks following visit 8 for a safety follow-up check. Procedures to be performed are reflected in Figure 3.

If a subject withdraws or is terminated early from the study, visit 9 procedures will be performed at the final study visit.

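### The safety comparison with placebo has no time window although placebo ends after Phase 1, and its EKG part cannot be made for completers

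*Combined protocol and SAP*

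**What the plan says.** Under Research Hypotheses, secondary outcome 2a reads "MSA adjunctive to ADT will demonstrate clinically acceptable safety and tolerability, compared to placebo, based on" five items: adverse events, blood pressure and pulse, weight, "significant changes in electrocardiogram", and the RSI. It names no phase, visit or period.

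Under Statistical Analysis, the outcomes are listed as "Safety outcome measures: adverse events, physical examinations, vital signs; blood pressure, orthostatic; EKG", followed by the RSI. No safety method or window is given. The analysis set is defined by "The Safety sample will include those randomized patients who received at least one dose of doubleblind study medication", without reference to phase or to the treatment being taken when an event occurs.

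The two phases last 21 days each. Group 1 takes MSA throughout. The other arm is described as "Group 2: PBO during Phase 1 followed by MSA during phase 2", and "Phase 2 study drug is dispensed at study visit 5". No one takes placebo after Phase 1.

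Fig. 3 schedules vital signs, weight and adverse events at every visit from V1 to V9, and the RSI from V1 to V8. EKG is scheduled at V1 and V9 only, and physical examination at V1 only. Study Procedures places V9 two weeks after V8, removes the blind at the end of V8, and gives early withdrawals the V9 procedures at their final visit.

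**The concern.** A claim of acceptable safety relative to placebo needs data from a period when one arm was on placebo. Here that period is V2 to V5. If events are counted or changes measured to the end of treatment, the contrast is between six weeks and three weeks of MSA. Similar results in the two arms would then say little about MSA against placebo, and any dilution would favour the tolerability claim.

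A Phase 1 window cannot simply be presumed. Where the plan does state when an outcome is compared, for the primary outcome under Study Design, it names the end of the trial, when both arms are on MSA.

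EKG is a different problem. For the other four items in 2a the data exist and only the window is missing. For EKG the schedule contains no on-treatment recording in Phase 1.

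**Working it through.** The plan gives no safety rate, margin or power to reproduce, so the check uses the visit schedule and then assumed risks.

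**1. Exposure, from the days in Fig. 3**

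| Point | Group 1, days on MSA | Group 2, days on MSA |
|---|---|---|
| V5 (day 21) | 21 | 0 |
| V8 (day 42) | 42 | 21 |

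V9 is on day 56, and 56 - 42 = 14 days after V8.

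**2. Adverse-event incidence (all risks assumed)**

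Let p0 and p1 be the 3-week risks of a first event on placebo and on MSA. Let m be the risk in weeks 4 to 6 for Group 1 subjects with no event so far. Assume no drop-out, and that Group 2 has risk p1 in its first three weeks on MSA.

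- Phase 1 difference: p1 - p0
- Whole study, Group 1: 1 - (1 - p1)(1 - m)
- Whole study, Group 2: 1 - (1 - p0)(1 - p1)
- Whole-study difference: (1 - p1)(m - p0)

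With p0 = 0.15 and p1 = 0.40, the Phase 1 difference is 25 points, and Group 2 over the whole study is 1 - 0.85 × 0.60 = 49%.

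| Risk on continued MSA | Group 1 | Difference |
|---|---|---|
| Constant, m = 0.40 | 1 - 0.60 × 0.60 = 64% | +15 points |
| Falls to m = 0.20 | 1 - 0.60 × 0.80 = 52% | +3 points |
| Falls to m = 0.10 | 1 - 0.60 × 0.90 = 46% | -3 points |

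Other assumed pairs (placebo/MSA) show the same pattern. Under constant risk, the Phase 1 difference shrinks from 15 to 12 points at 5%/20%, from 20 to 14 at 10%/30%, from 30 to 18 at 10%/40%, and from 20 to 12 at 20%/40%. If the excess falls entirely in the first three weeks on MSA (m = p0), the whole-study difference is 0 in every case. At 10%/30% with 20 per arm and a two-sided 5% test (assumed), approximate power is 35% in Phase 1 and 14% over the whole study under constant risk.

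**3. Continuous measures (blood pressure, pulse, weight, RSI)**

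Let E be the mean effect after three weeks on MSA.

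- If the effect plateaus within three weeks, the expected difference at V8 is E - E = 0.
- If it accumulates linearly, the difference at V8 is 2E - E = E, the same as at V5, and nothing is lost.

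**4. EKG and physical examination**

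The V1 EKG precedes study drug. The next scheduled EKG is V9, by which time Group 2 completers have had 21 days of MSA, Group 1 completers 42, and the blind is off. No scheduled recording falls between V2 and V8. Whether V9 is on or off drug is also unclear. Study Procedures (visits 6-8) and the dosing section describe tapering from V8, while Study Procedures also provides a one-month prescription at the current dose at V8. Physical examination has a V1 value and no scheduled later one, apart from whatever is recorded outside the schedule.

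**The case against.** The strongest reply is that the plan is silent rather than wrong. Nothing says safety will be pooled over both phases. Placebo exists only in Phase 1, so a comparison with placebo is naturally read as a Phase 1 comparison. Adverse events, vital signs, weight and the RSI are all collected at V3 to V5, so that comparison can be made from planned data. This stands, and it limits the point for those four items to an unstated window.

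A reader might infer that the design hides the drug's harms, or that similar whole-study rates would be declared acceptable. The documents do not support that: they state no pooled analysis, no safety test and no acceptance criterion.

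A reader might also infer that EKG is measured only after both arms have had MSA, or never on placebo. That is too absolute. There is a screening EKG, and a Group 2 subject who leaves during Phase 1 has an EKG at the final visit without having taken MSA. However, such subjects are selected by having withdrawn, so they cannot support a randomized comparison.

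Finally, quoting only the -3 to +3 result would be one-sided. It assumes early-onset harms, and the same inputs under constant risk leave 15 points.

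**Conclusion.** The point holds in two parts.

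- **Window.** The comparison with placebo in hypothesis 2a has no stated period, in a design where placebo stops at the end of Phase 1. The loss from a whole-study comparison ranges from none (a linearly accumulating continuous change) to all (an early-onset excess or an early plateau). In the worked example, 25 points become 15, or about -3 to +3. These risks are assumptions, because the documents give none. Any dilution would make MSA look more like placebo.
- **EKG.** The stated comparison cannot be delivered for completers under the Fig. 3 schedule. This does not depend on any assumed rate, and choosing a window does not repair it.

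Physical examination is a smaller inconsistency. It is not part of hypothesis 2a, but it is listed as a safety outcome measure with no scheduled follow-up. Correcting the efficacy endpoint would not settle any of this, because 2a is a separate statement about separate data.

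**What to change.** Make these changes in the hypothesis and the statistical section:

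- State that safety comparisons with placebo use V2 to V5. Count adverse events with onset before Phase 2 drug is started, using each subject's actual start date because visits may move by 3 days either way. For blood pressure, pulse, weight and RSI, use change from baseline to V5.
- Report Phase 2 separately as uncontrolled MSA exposure, by weeks on drug.
- Remove EKG from the outcomes compared with placebo and report it as an uncontrolled V1-to-V9 change.
- Remove physical examination from the safety outcome measures.
- Reconcile the tapering from V8 with the one-month prescription at the current dose, so that it is clear whether the V9 EKG is on or off drug. Until then, even a pre-post EKG change is hard to interpret.

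The cost is wording. The Phase 1 data are already collected weekly and no new procedure is needed. The plan gives up a placebo-controlled EKG claim, but the schedule cannot support that claim anyway. Keeping it would require a recording at the end of Phase 1, which would be a new procedure.

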In elderly patients, methylphenidate has been found to successfully augment citalopram; 8 of 10 patients so treated showed clinically significant improvement, although improvement did not necessarily occur previous to week 8 (Lavretsky & Kumar, 2001).found that 5 of 6 patients randomized to active citalopram and MPH achieved remission of symptoms (HAM-24 \leq 10) compared with none of those randomized to the CIT plus placebo group so remitting (2006). Concordantly, Masand et al (1998) found in their 7-case series that every patient (previously responding only partially to a 2nd generation AD) achieved a marked improvement, and we note, especially in the symptoms of apathy and fatigue, when augmented with a stimulant.(2009) found in their review of TRD augmentation studies that symptoms rated by the Hamilton and MADRS scales do not generally improve with stimulant augmentation, however, CGI scores do improve, as do measures of sleep and energy.

Selegiline, an MAO inhibitor, through certain of its metabolites (L-amphetamine and Lmethamphetamine) is known to increase DA synthesis. Feinberg (2004) reviews the efficacy of augmentation of MAOI ADs with selegiline and proposes the practice may have some clinical utility, including in cases of TRD. The author notes that the availability of transdermal selegiline would decrease the potential for abuse of add-on stimulant medication. Again, further study is recommended by the author.

Ng's 2009 report of his survey of New Zealand psychogeriatricians finds that stimulants are consistently and successfully, if not frequently utilized in that population to augment treatment-resistant cases. He later elaborated (2009) that such stimulant augmentation improved specifically fatigue and apathy, promoting wakefulness, alertness, and possible mood enhancement. In a further elaboration, Ng (2009) explores whether psychostimulant medication may have efficacy among treatment-resistant cases across a broader demographic. The above findings are consistent with this study's assertion that depression is usefully conceptualized as a disorder comprised of a constellation of symptom domains, each domain potentially responding best to a particular treatment strategy.

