Inclusion Criteria:

- 1) Male or female outpatients between the ages of 18-70.
- Subject must meet criteria for single or recurrent, non-psychotic episode of MDD according to DSM-IV-TR diagnosis, as determined by Structured Clinical Inventory of Depressive Symptoms (SCID) and confirmed by assessment of investigator.
- 3) Current depressive episode must be at least 8 weeks in duration.
- 4) HDRS-17 score \geq 14 at both the screen and baseline visits.
- 5) Subject must have been receiving an adequate, stable dose of ADT, based on Massachusetts General Hospital-Antidepressant Treatment Response Questionnaire (MGH-ATRQ).
- 6) Subject must be responding inadequately to his/her current monotherapy ADT in the current major depressive episode (MDE).
- 7) Subjects must be able to read and understand English and be able to provide written informed consent.
- 8) Subjects must be considered reliable, able to comply with protocol requirements and understand the risks and benefits, per the investigator's clinical judgment.
- 9) Female subjects of childbearing potential must agree to use adequate form of birth control throughout the course of the study.

Exclusion Criteria:

- 1) Inadequate response during the current episode to more than 3 adequate trials of an ADT, as defined by the MGH-ATRQ.
- 2) Psychiatric hospitalization within the last 6 months.
- 3) Presence of cognitive disorder(s), bipolar disorder, Axis II pathology or other condition that investigator believes would interfere with participation in the study.
- 4) Substance use disorder, current (as defined by DSM-IV-TR SCID) or positive results on urine drug screen or laboratory blood tests.
- 5) Risk to self or others.
- 6) The presence of any medical condition, current or past, stable or unstable, that contraindicates the use of antidepressant medication or mixed amphetamine salts medication as determined by clinician's judgment.
- 7) Clinically significant abnormal findings on physical exam, EKG or laboratory tests; current unstable, untreated hypertension in the opinion of the investigator; history of cerebrovascular accident (CVA) or seizure disorder (other than febrile childhood seizure).
- 8) Allergies and/or adverse drug reactions to MSA.
- 9) Failure to respond to an adequate trial of MSA adjunctive to ADT in the current episode.
- 10) Subjects taking narcotics, herbal/homeopathic remedies and/or other substance with psychotropic activity, based upon clinical judgment of study investigator.

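### Hypothesis 2d claims better functioning than placebo, but half of its instruments are symptom or pleasure scales, none is titled cognitive, and the HDRS is never rated on placebo

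*Combined protocol and SAP*

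**What the plan says.** Under Research Hypotheses, Secondary outcome, item 2d states that the group given MSA on top of ADT "will show statistically significantly improvement in overall functioning (work, social and cognitive) when compared to the group treated with PBO and ADT". Nine entries follow as its measures. The first two are "Total and individual item scores from the HDRS-17 and -28" and "Maier and other subscale scores from the HDRS-17 and -28". The others are SANS, HSQ 2.0, SF-36, EPI, EWPS, SDS and FASD.

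Residual depressive symptoms have a hypothesis of their own, 2c (PGI, QIDS-16, CGI-S and CGI-I), and the MADRS is under 2b. The MGH-CPFQ is under hypothesis 1, with its items under 2b.i. It is not under 2d.

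The Statistical Analysis section names the key secondary endpoints: MADRS change, MADRS remission, MGH-CPFQ items, CGI-S, CGI-I and QIDS. It does not mention the 2d measures and gives no composite, ranking or decision rule for them.

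**The concern.** Hypothesis 2d makes a claim about one construct, functioning, and names three domains: work, social and cognitive. Much of its list measures something else, and one of the three domains has no evident measure. Since nothing says which entries carry the claim, a favourable result on a depression, pleasure or fatigue scale would fit the hypothesis as worded even if the work and disability scales showed no difference. The reported conclusion would then not follow from its evidence.

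The claim is also explicitly one against placebo. For part of the list, the visit schedule has to be checked to see whether such a comparison exists.

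**Working it through.** No sample-size, power or alpha figure bears on this point. The check is a count and a reading of the visit schedule.

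**Step 1. Classify the nine entries**, by title and by how the protocol itself describes the construct.

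| Entry | Measure | Class | Basis |
|---|---|---|---|
| i | HDRS totals and items | symptom | Background (see step 2) |
| ii | HDRS subscales | symptom | same instrument as i |
| iii | SANS | symptom | title |
| iv | HSQ 2.0 | health status | title |
| v | SF-36 | health status | title |
| vi | EPI | pleasure | title |
| vii | EWPS | work function | title |
| viii | SDS | disability | title |
| ix | FASD | symptom (fatigue) | title |

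By list entry: symptom or pleasure = i, ii, iii, vi, ix = 5 of 9; function or health status = iv, v, vii, viii = 9 − 5 = 4 of 9. By distinct instrument, with i and ii merged: 9 − 1 = 8 instruments, of which 5 − 1 = 4 are symptom or pleasure scales and 4 are function or health-status scales. Titled as cognitive: 0 on either count.

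**Step 2. Check that the protocol separates these constructs.** The Background on stimulant augmentation says that "symptoms rated by the Hamilton and MADRS scales do not generally improve with stimulant augmentation", so it treats the Hamilton scale as a rating of symptoms. The same part calls apathy and fatigue symptoms, and Mechanism of Action puts loss of pleasure among the core symptoms of depression. The section on treatment-refractory depression links lingering symptoms to poorer psychosocial functioning, which makes symptoms and functioning two different things. The classification in step 1 therefore follows the protocol's own usage.

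**Step 3. Check where cognition is measured.** The MGH-CPFQ is the only instrument with cognition in its title. Fig. 3 schedules it at every visit from V1 to V8. The trial therefore has a candidate measure, but 2d does not refer to it.

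**Step 4. Check whether each entry can be compared with placebo.** Fig. 1 and Study Procedures give Group 2 placebo in Phase 1 (assessed at V3 to V5) and MSA in Phase 2 (V6 to V8). Fig. 3 marks the HDRS at V1, V2 and V8 only.

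- At V8, Group 1 has had two 21-day phases of MSA (2 × 21 = 42 days). Group 2 has had one phase of placebo and one of MSA (21 days of MSA). The HDRS contrast at V8 is longer against shorter MSA treatment, not MSA against concurrent placebo.
- Subjects who leave early have the V9 procedures, which do not include the HDRS. With no HDRS between V2 and V8, there is also no earlier post-randomization value for LOCF to carry forward.
- EWPS, SDS, SF-36 and HSQ 2.0 are marked at every visit from V1 to V8, as are SANS, EPI and FASD. All of these have a placebo comparison at V3, V4 and V5.

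Entries i and ii thus cannot support the contrast that 2d states. The four function or health-status scales can.

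**The case against.** The strongest reply is that this is a labelling matter in lower-tier outcomes of a 40-subject study. Four real function or health-status scales are on the list, no 2d measure is a key secondary endpoint, and the primary analysis, safety and data collection are untouched. The Background also reports that Hamilton symptoms do not generally respond to stimulants, which makes a misleading HDRS result less likely. All of this stands and limits the size of the point. It does not remove it: the same Background reports gains in energy, fatigue and apathy, so a favourable FASD result is plausible, and under 2d it would count as better functioning.

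A reader might infer several stronger things that the documents do not support.

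- *That most of the instruments are not functional.* Five of nine entries is correct for the list as printed, but two of the five are the same scale. By instrument it is half.
- *That cognition is unmeasured, or that no listed scale has cognitive content.* The MGH-CPFQ is collected throughout. The documents do not describe the content of the 2d scales, and the additional HDRS subscales are unnamed. Only the statement about titles is safe.
- *That a symptom gain will be reported as a functional gain.* The plan permits this; it does not prescribe it.
- *That the number of HDRS items tested measures this defect.* That is a multiplicity question. It would be the same wherever the items were listed, and the documents state no significance level for it.
- *That HDRS scores are biased here because the HDRS-17 is an entry criterion.* The threshold applies before randomization and to both groups alike, so it does not by itself distort a comparison between them.

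**Conclusion.** The point holds as a mismatch between claim and measures. Four of the eight instruments under 2d (five of nine entries) measure symptoms or pleasure, none is titled as cognitive, and no rule says which entries decide. A symptom change could therefore be reported as improved functioning. Separately, the HDRS entries offer no concurrent placebo comparison, although 2d claims one.

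The impact is moderate. It concerns what may be concluded about functioning and does not reach the primary outcome or any key secondary endpoint. The conclusion assumes that instruments are fairly classified by their titles and by the protocol's own descriptions, and that the visit marks in Fig. 3 are as printed.

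**What to change.** Reword 2d and place its measures as follows.

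- **Functioning:** keep EWPS, SDS, SF-36 and HSQ 2.0. State that they are compared between MSA and PBO in Phase 1 (V3 to V5). Name one in advance as the basis for the claim; which one is the sponsor's choice.
- **Cognition:** refer this part to the MGH-CPFQ, already collected at V1 to V8, and state which score is meant, since the documents do not describe its item structure. Otherwise delete the word from 2d.
- **SANS, EPI, FASD:** move them to the symptom hypotheses (2b or 2c).
- **HDRS totals, items and subscales:** move them there too, as a descriptive V8 measure with no claim of superiority over concurrent placebo. Because 2b states a comparison with placebo, the HDRS would need this qualification if listed under it.

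The cost is the rewording of the affected hypotheses. No visit, instrument or data item is added. The downside is that fewer scales can support the functioning claim.
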